3.2 Study Design and Scope

This is a prospective, multicenter, non-randomized registry/observational study. All subjects who meet inclusion criteria, do not meet exclusion criteria, sign an IRB/EC approved informed consent, complete a Baseline visit prior to device implant and have an attempted implant of the SJM Quadra Allure MP, Quadra Assura MP, or newer SJM CRT MP device will be considered enrolled in the study. MPP programming guidelines are provided in Appendix I. Patients will be followed for 12 months after implant. Data will be collected at post-implant (within 30 days of successful CRT device implant), 3, 6, 12 months and during any unscheduled follow-up visit. At 12 months, the responder rate will be evaluated among the following groups:

- MPP Group: MPP ON within 1 month post implant and then continuously programmed ON until 12 months (i.e., MPP ON for months 1-12 continuously)
- Treatment Strategy (BiV/MPP) Group: MPP ON at the 12-month study visit and for at least 3 continuous months prior to 12-month assessment (i.e., BiV ON at some point in months 1-9 and MPP ON for months 10-12)
- BiV Group: MPP OFF at the 12-month study visit and for at least three continuous months prior to 12-month assessment (i.e., BiV ON for months 10-12)
- Other Pacing Group: Other pacing schemes not covered above (Retrospective categorization implemented based on the usage of MPP or BiV for 12 months)

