5.5 SCHEDULED FOLLOW-UPS

The schedule of follow-up visits is based on the date of successful SJM CRT MP system implant.

Clinical Investigational Plan

Table 3.0 outlines the time window permitted for each of the study visits.

Table 3: Study Time Interval Windows

3 Months	6 Months	12 Months
± 14 days	± 30 days	± 45 days

All subjects will be followed at 3, 6 and 12 months after the date of successful implant. During each follow-up visit, NYHA class and Patient Global Assessment (PGA) will be completed. Refer to section 5.2. All patients will also complete QOL questionnaires (MLWHF and EQ-5D) during each scheduled follow-up visit. If a 2D-Echocardiogram was conducted as part of the patient’s standard of care since the last visit, LVEF and LVESV values will be collected on the Follow-up CRF.

The following device testing will be conducted:

- RV-LV conduction tests using both RV sense and RV pace configurations

*Note: If patient is pacemaker dependent, conduction tests using RV sense are not required.

For the RA and RV leads:

- Capture threshold testing
- Lead impedance
- Signal amplitude

*Note: If patient is in atrial fibrillation or atrial flutter, RA electrical measurements are not required.

*Note: If patient is in complete heart block or is pacemaker dependent, RV sensing amplitude is not required.

For the LV lead:

The following testing must be performed for the programmed LV lead vector(s)-

- Capture threshold testing
- Lead impedance

Final BiV and MPP programming at all visits is per physician’s discretion. MPP programming guidelines are provided in Appendix I.

A Follow-up CRF, MLWHF and EQ-5D questionnaires should be completed using the EDC system. If a patient had an inpatient hospital stay, ER visit, observational visit, outpatient visit, urgent care visit, or unscheduled office visit for cardiovascular reasons only since the last visit,

Clinical Investigational Plan

a Health Care Utilization / Hospitalization CRF should be completed. All forms should be submitted to St. Jude Medical using the EDC system.

The following device session records must be downloaded and sent to St. Jude Medical using the EDC system.

- Initial and Final Programmed Parameters
- Real-Time Measurements and Trends for all implanted leads
- Capture threshold testing results for RA, RV and LV lead
- All “new” stored IEGM(s) since previous session

Once the new IEGM(s) are downloaded and exported, clear all IEGM(s) and diagnostics.

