12.1 STATISTICAL DESIGN, HYPOTHESES, METHOD AND ANALYTICAL PROCEDURES

This is a prospective, multicenter, non-randomized registry/observational study. Analysis of the study objectives will be summarized using data collected upon 12-month follow-up visit by the groups defined in section 3.2. The objectives of this study will be summarized as the follows:

- Overall CRT response rate at 12 months will be summarized by percentages with a 95% confidence interval using exact method for binomial distribution.
- QOL, LVEF, and LVESV at baseline, 3, 6, and 12 months will be summarized by means (\pm standard deviation), median and range.
- Programming timing and workflow between implant and 12 months will be summarized by frequency and percentage for categorical data.
- Rates of heart failure (HF) hospitalization events at 12 months, cardiovascular hospitalizations at 12 months, and HF 30-day hospitalization rates will be summarized using Kaplan-Meier method.
- Costs associated with HF-related health care utilizations at 12 months will be summarized by means (\pm standard deviation), median and range.
- All-cause mortality at 12 months will be summarized using Kaplan-Meier method.

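### The 3- and 6-month QOL, LVEF and LVESV summaries appear to be sorted by groups that depend on later programming, so the early MPP and BiV rows can differ without a pacing effect

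*Combined protocol and SAP*

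**What the plan says.** The opening of section 12.1 sets the grouping: "Analysis of the study objectives will be summarized using data collected upon 12-month follow-up visit by the groups defined in section 3.2". One of the bullets that follow says that "QOL, LVEF, and LVESV at baseline, 3, 6, and 12 months will be summarized by means" with standard deviation, median and range. No separate rule says how the 3- and 6-month values are to be grouped.

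Section 3.2 defines the groups by programming history:

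- The MPP Group requires the following: "MPP ON within 1 month post implant and then continuously programmed ON until 12 months (i.e., MPP ON for months 1-12 continuously".
- The Treatment Strategy Group, labelled BiV/MPP, requires MPP on at 12 months and for the three months before, glossed as "i.e., BiV ON at some point in months 1-9 and MPP ON for months 10-12".
- The BiV Group is defined as "MPP OFF at the 12-month study visit and for at least three continuous months prior to 12-month assessment (i.e., BiV ON for months 10-12". Months 1 to 9 are unrestricted.
- The Other Pacing Group takes the remaining histories, classified retrospectively on 12 months of use.

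Programming can change during follow-up. Section 5.5 leaves "Final BiV and MPP programming at all visits" to the physician, and section 8.0 notes that MPP can be turned off in a patient who does not benefit. Section 5.2 has responder status assessed at 3 and 6 months as well as at 12. The mode in use at each scheduled visit is recorded: section 5.5 requires "Initial and Final Programmed Parameters" to be downloaded, and section 5.6 asks for session records from unscheduled reprogramming visits.

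**The concern.** A value measured at month 3 or 6 is placed in a row by decisions taken after it, and possibly because of it. Two things follow.

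First, the BiV row may contain early values taken on MPP. A patient on MPP at months 3 and 6 who is switched off at month 8 and stays off belongs to the BiV Group, and both early values go there.

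Second, the MPP row has the right mode but is selected on the future. A patient who feels poorly on MPP at month 6 and is switched off leaves the row, so the row keeps those who were doing well enough to continue.

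The Treatment Strategy row is different. Its name and definition declare a mixed history, so its early values are not mislabelled, although they should not be read as MPP values.

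Section 3.3 asks for an understanding of the impact of MPP on QOL, LVEF and LVESV. Early columns with rows headed MPP and BiV invite that use.

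**Working it through.** **1. What the definitions permit.** The plan states no figure to reproduce, so the first check is logical. Code each of 12 months as MPP on or off, giving 2^12 = 4,096 histories, and assign each to a section 3.2 group.

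| Group | Histories | Mode at months 3 and 6 |
|---|---|---|
| MPP | 2 | MPP at both in all |
| BiV | 512 | MPP on at one or both in 384; off at both in 128 |
| Treatment Strategy | 510 | BiV at one or both in 384; MPP at both in 126 |
| Other | 3,072 | any |

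These counts show what is allowed, not how often it occurs. Mismatch is impossible in the MPP Group, and possible but not certain in the BiV Group.

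**2. Size of a false difference at month 6.** All inputs here are assumptions; the readable text gives none of them, and the sample size section is redacted.

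- Month-6 Minnesota score: normal, mean 35, SD 22, limited to the questionnaire's range of 0 to 105 (21 items scored 0 to 5; higher is worse). Mode has no effect on it.
- Share on MPP up to month 6: q = 0.3, 0.5 or 0.7, independent of the score.
- Switching between months 6 and 9, with probability p_w in the worst third of scores and p_r in the rest: A 0.30/0.10, B 0.40/0.10, C 0.50/0.05.

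Mean of the worst third: 35 + 22 × 1.091 = 59.0. Mean of the rest: 35 − 22 × 0.545 = 23.0, raised to 23.8 by the floor at 0. The gap is 35.2.

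The overall switching rate is s = p_w/3 + 2p_r/3. The worst third makes up (p_w/3)/s of switchers and ((1 − p_w)/3)/(1 − s) of stayers. Switchers therefore exceed stayers by D = (difference of those shares) × 35.2.

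- A: s = 0.167; D = (0.600 − 0.280) × 35.2 = 11.3
- B: s = 0.200; D = (0.667 − 0.250) × 35.2 = 14.7
- C: s = 0.200; D = (0.833 − 0.208) × 35.2 = 22.0

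The MPP row holds MPP stayers. The BiV row holds BiV stayers plus MPP patients switched off; the latter are a fraction f = qs / [qs + (1 − q)(1 − s)]. With no mode effect, both kinds of stayer have the same mean, so BiV minus MPP = f × D.

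| q | f (A, B, C) | BiV minus MPP, points (A, B, C) |
|---|---|---|
| 0.3 | 0.079, 0.097, 0.097 | 0.9, 1.4, 2.1 |
| 0.5 | 0.167, 0.200, 0.200 | 1.9, 2.9, 4.4 |
| 0.7 | 0.318, 0.368, 0.368 | 3.6, 5.4, 8.1 |

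The MPP row looks about 1 to 8 points better, and 8% to 37% of the BiV row was measured on MPP. In this model the Treatment Strategy row sits D = 11 to 22 points above the MPP row, but only because every patient in it switched after month 6.

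**3. Switching unrelated to score.** With p_w = p_r = 0.20, D = 0 and the false difference vanishes, although f is still 10% to 37%. If MPP then had a constant true effect, the early contrast would shrink to (1 − f) of its size: 90% at f = 10%, 75% at 25%, 50% at 50%.

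**4. Labelling by mode in force.** In the model of step 2 this gives a difference of about 0, because the switch comes after the measurement. That result depends on nobody having switched on outcome earlier. Applying the same switching rule at month 3 as well, with an assumed correlation of 0.5 to 0.7 between month-3 and month-6 scores, simulation gives at month 6:

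| q | BiV minus MPP by mode in force | BiV minus MPP by section 3.2 group |
|---|---|---|
| 0.3 | about −1.3 to −4.1 | 1.7 to 4.8 |
| 0.5 | about 0 | 2.8 to 6.8 |
| 0.7 | about +1.3 to +4.2 | 4.2 to 9.8 |

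The month-3 column by mode in force stays near 0, since in this model no outcome-driven switch precedes it.

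**The case against.** Section 12.1 does not say outright that the early values are tabulated by group. The grouping phrase is in the lead-in, which speaks of data from the 12-month visit, and section 3.2 introduces the groups for the 12-month responder rate. This stands as a point about wording. But if the groups apply only to 12-month data, the plan has no grouping for the 3- and 6-month values, and 12.1 still needs a sentence.

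The summaries are descriptive. Section 12.1 plans no between-group test, and a trajectory by eventual strategy is a legitimate description of those groups. The programming summary in 12.1 gives some context on when modes changed. LVEF and LVESV are recorded only when a standard-of-care echocardiogram exists, so those columns may be sparse under any label. All of this is fair and limits the weight of the point; it does not tell a reader of the BiV row which mode the early values came from.

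The size rests wholly on assumed inputs and on switching that follows outcome. That is correct. Section 8.0 makes such switching plausible but gives no rate.

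A reader might infer that every group label is fixed by months 10 to 12 and that early values are generally filed under the wrong mode. The documents do not support this: the MPP Group is defined over months 1 to 12, the Treatment Strategy label declares both modes, and a BiV Group patient may have been on BiV throughout. Nor should one infer that relabelling makes the early comparison unbiased; step 4 shows that it need not.

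**Conclusion.** The point holds for two rows. Early values in the BiV row may come from MPP, and the MPP row excludes patients later switched off. With outcome-driven switching and no true effect, the month-6 table could show MPP better by about 1 to 8 Minnesota points under the assumptions in step 2. If switching is unrelated to outcome the false difference is about 0, but the BiV row remains mixed. The true size cannot be set from the documents.

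The effect is on how the early columns are interpreted. No error rate is involved, and the 12-month responder analysis is not affected by this point. It is a cheap improvement, not a flaw that undermines the study.

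**What to change.** In section 12.1, state that 3- and 6-month QOL, LVEF and LVESV are summarised by the pacing mode in force up to that visit, in three categories: MPP throughout, BiV throughout, mixed. Define the interval explicitly, for example from the previous scheduled visit. Derive the category from the initial programmed parameters at the visit and any unscheduled session records in between. Use the section 3.2 groups for the 12-month values. If trajectories by section 3.2 group are also shown, print beside each row the number of patients on each mode at 3 and 6 months.

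Add a note that the early columns are descriptive: classification by later decisions is removed, but selection of who starts MPP and outcome-driven switches before the visit are not.

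The cost is a short addition to 12.1 and one derived variable from records already downloaded, with no new data or patients. The downside is that group sizes will differ between the early and 12-month columns.

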3.3 Objectives

The objective of this post-market study is to understand the use of the MPP technology in real-world clinical practice. The study should provide an understanding of the impact of MPP technology on:

Clinical Investigational Plan

- Overall CRT response rate measured by CCS. (A responder is defined as improved or unchanged from baseline and non-responder is defined as worsened from baseline.)
- QOL, LVEF, if available and LVESV, if available
- Programming timing and workflow
- Rates of HF hospitalization events, cardiovascular hospitalizations, and HF 30-day hospitalization rates
- Costs associated with HF-related healthcare utilizations
- All-cause mortality

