5.2 Evaluation of responder status

Patients' responder status will be assessed at 3, 6 and 12 months post implant using the CCS. The CCS includes four components: NYHA class, Patient Global Assessment (PGA), HF events, and cardiovascular death.²¹

The **NYHA Class assessment and PGA** are determined by a designated assessor interviewing patients about their symptoms. Specifically, the PGA will be a single interview question asking the patient to categorize how they feel compared to their previous visits as either:

- Markedly better
- Better
- No change
- Worse
- Markedly worse

At the 3, 6 and 12-month visits, a PGA will be conducted to evaluate how the patient feels compared before having the CRT system implanted.

In this trial, a **HF event** is defined as any one of the following when the subject has symptoms and/or signs consistent with congestive heart failure:

- Hospitalization for HF \geq 24 hours
- Clinic or hospital visit for HF < 24 hours (i.e. outpatient treatment, observational care, ER, Urgent Care and physician's office visit) requiring administration of IV diuretics, inotropes, and/or vasodilators

Finally, **cardiovascular death** is defined as sudden unexpected death; heart failure death; myocardial infarction related death; or 'other' death, such as deaths due to pulmonary embolism, peripheral thromboembolism, stroke, vascular procedure, or other major cardiovascular event.

Using the CCS and decision algorithm described in section 5.2.1 patients are categorized as Improved, Worsened or Unchanged based on the following rules:

- “Improved” – patients demonstrating:
 - At least a one-class improvement in NYHA Class OR improvement by PGA (“better” or “markedly better”)
AND
 - No HF events as described above
AND
 - No cardiovascular death
- “Worsened” – patients demonstrating:
 - Worsening in NYHA Class OR worsening by PGA (“worse” or “markedly worse”)

OR

[figure not shown]

Clinical Investigational Plan

- Presence of HF events as described above
OR
 - Cardiovascular death
- “Unchanged” – patients neither “Improved” nor “Worsened”.

Patients who are “Improved” or “Unchanged” using the above definition will be grouped together as Responders. Patients classified as “Worsened” will be considered Non-Responders.

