6.0 CLINICAL EVENTS/ HOSPITALIZATIONS

Any clinical event resulting in an inpatient hospital stay, ER visit, observational visit, outpatient visit, or urgent care visit for cardiovascular reasons must be reported to St. Jude Medical. Detailed source documentation surrounding the clinical event should also be sent to St. Jude Medical using the EDC system. This may include:

- Emergency department notes
- Physician consultation notes
- Medication records and logs
- Admission notes
- Laboratory results and summary details
- Discharge summary
- Operative notes
- Clinician progress notes
- X-ray reports
- Diagnostic test reports

A Health Care Utilization /Hospitalization CRF and Medication CRF (if applicable) should be completed for each clinical event/ hospitalization and submitted along with supporting documentation to St. Jude Medical using the EDC system.

Clinical Investigational Plan

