6.1 HEALTH CARE ECONOMIC DATA

To assess potential differences in costs for heart failure-related health care utilizations among the groups described in section 3.2, billing records (i.e., UB-04 and CMS-1500 for centers in the United States) will be collected on a Health Care Utilization/ Hospitalization CRF.

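### The 12-month HF and cardiovascular hospitalization summaries use Kaplan-Meier alone, so repeat admissions, although collected, are not counted in them

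*Combined protocol and SAP*

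**What the plan says.** Section 12.1 puts three hospitalization measures in one bullet. It opens with "Rates of heart failure (HF) hospitalization events at 12 months" and closes with "cardiovascular hospitalizations at 12 months, and HF 30-day hospitalization rates will be summarized using Kaplan-Meier method". The readable text names no other method for hospitalization: no count, no rate per patient-year, no mean cumulative function and no recurrent-event model.

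The objective in section 3.3 is worded "Rates of HF hospitalization events, cardiovascular hospitalizations, and HF 30-day hospitalization rates". Neither section says what a rate is. Section 12.1 also uses the word for a proportion: "Overall CRT response rate at 12 months will be summarized by percentages".

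The data hold more than first events. Section 6.0 says that a utilization form "should be completed for each clinical event/ hospitalization". Two other summaries draw on these events. In section 5.2 the Clinical Composite Score classes a patient as worsened on "Presence of HF events as described above". Section 6.1 gives the purpose of the billing records: "To assess potential differences in costs for heart failure-related health care utilizations among the groups described in section 3.2"; section 12.1 then summarizes those costs by mean, standard deviation, median and range.

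Section 12.1 states no time origin. Implant is the natural inference, since section 3.2 follows patients for a year from implant and section 5.5 says "The schedule of follow-up visits is based on the date of successful SJM CRT MP system implant".

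**The concern.** A Kaplan-Meier estimate at 12 months gives the share of patients with at least one event. A patient admitted four times counts the same as one admitted once. The study wants to understand the effect of MultiPoint Pacing on hospitalization, and repeat admissions are part of that burden. They are collected, yet the plan never reports how many there were.

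A second, smaller matter is death. A patient who has died can no longer be admitted. Kaplan-Meier with deaths censored treats that patient as still at risk, and so overstates the proportion hospitalized in any set that contains deaths.

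**Working it through.** **Step 1. Where a repeat admission would appear.** Taking each readable summary in turn:

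| Summary | Repeat HF admission | Repeat non-HF cardiovascular admission |
|---|---|---|
| HF hospitalization at 12 months (Kaplan-Meier) | adds nothing | out of scope |
| Cardiovascular hospitalization at 12 months (Kaplan-Meier) | adds nothing | adds nothing |
| HF 30-day rate | counted only if the clock starts at an HF discharge | out of scope |
| Composite score | adds nothing (presence only) | out of scope |
| HF-related cost | raises the mean; number not shown | out of scope |

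**Step 2. Share of admissions unused.** The plan states no hospitalization figure to reproduce, so all inputs here are assumed. Let p be the 12-month risk of a first event, with complete follow-up, no deaths and Poisson admissions within patient. Patients' rates either are equal or vary with a gamma distribution of shape k. Mean admissions per patient are

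- no variation: mu = -ln(1 - p)
- gamma shape k: mu = k × ((1 - p)^(-1/k) - 1)

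and the unused share is 1 - p/mu.

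| p | no variation | k = 2 | k = 1 | k = 0.5 |
|---|---|---|---|---|
| 10% | 5.1% | 7.6% | 10.0% | 14.7% |
| 20% | 10.4% | 15.3% | 20.0% | 28.9% |

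Example: p = 20% and k = 1 give mu = 1/0.8 - 1 = 0.25. Per 100 patients, 20 are admitted and there are 25 admissions. A simulation that added 5-15% mortality, independent of the admission rate, gave 5.0-28.7%. A wider grid (0.10-0.40 admissions per patient-year, no variation up to k = 0.25) gave 4.8-46.9%.

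**Step 3. One Kaplan-Meier value, several burdens.** A 12-month value of 15% fits -ln(0.85) = 0.163 admissions per patient-year without variation. With k = 0.25 it fits (0.85^(-4) - 1)/4 = 0.229.

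**Step 4. Deaths.** Assume constant, independent hazards l1 = -ln(1 - hospitalization risk) and l2 = -ln(1 - mortality). Then 1 minus Kaplan-Meier is the hospitalization risk itself, 20% here, while the cumulative incidence is l1/(l1 + l2) × (1 - exp(-(l1 + l2))).

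| Mortality | Cumulative incidence | Overstatement |
|---|---|---|
| 0% | 20.00% | 0 |
| 5% | 19.51% | 0.49 points |
| 10% | 19.02% | 0.98 points |
| 15% | 18.52% | 1.48 points |

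For 5%: l1 = 0.2231, l2 = 0.0513, and 0.2231/0.2744 × 0.24 = 0.1951.

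In section 3.2 the MPP, Treatment Strategy and BiV groups all require pacing status up to or at 12 months. They contain only survivors to that point, so the overstatement there is zero. Section 12.1 also plans an all-cause mortality summary, so some set must include the deaths, but neither section says which.

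**Step 5. Interval for a total rate.** Under the gamma model the variance of the count is (1 + mu/k) times its mean. A naive Poisson 95% interval then covers 94.4% at p = 10%, k = 2 (factor 1.054). At p = 20%, k = 0.5 (factor 1.5625) it covers 88.3%. A total-event rate therefore needs an interval that allows for clustering.

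**The case against.** The strongest reply is that nothing here is wrong. The readable plan is descriptive and tests no hypothesis. Time to first hospitalization is a legitimate summary, no passage promises a count, and naming Kaplan-Meier at 12 months already points to a cumulative probability. All of that stands. A reader might infer that the word rate commits the plan to admissions per patient-year and that section 12.1 contradicts its own objective. The documents do not support this, because the same section calls a percentage of responders a rate.

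A reader might also infer that repeat admissions are lost altogether. They are not: repeat HF admissions enter mean cost, and they are the outcome of the 30-day measure if it runs from a discharge. The gap is confined to the two 12-month summaries. It is complete only for repeat non-HF cardiovascular admissions.

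Finally, it is tempting to put all deaths in the Other Pacing Group. If overall mortality were 10% and that group held 20% of patients, half of the group would die (0.10/0.20). The cumulative incidence would then be 14.61% against 20%, a difference of 5.39 points. Section 3.2 does not support that placement. It sorts patients by pacing over 12 months, which someone who dies early does not have, so such patients could equally be unclassified. Nor does section 12.1 explicitly plan a pooled hospitalization curve.

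What survives the reply is that the data for a count are collected, no readable passage uses them for one, and adding one is cheap.

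**Conclusion.** The point holds as an inexpensive improvement. Followed in the ordinary way, section 12.1 reports the proportion with a first HF or cardiovascular admission and leaves the number of admissions unreported. The text never says first event; that follows from standard use of the method. At an assumed first-event risk of 10-20%, about 5-29% of admissions would be unused. The documents supply neither hospitalization nor mortality rates, so this shows direction and rough scale only.

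The overstatement from censoring deaths is about 0.5-1.5 points at an assumed 20% hospitalization and 5-15% mortality. It arises only in a set that includes deaths, and is nil in groups limited to 12-month survivors. The effect is on what is reported; no planned test in the readable text is affected. The missing origin of the HF 30-day rate is a matter for clarification and adds no weight to the finding.

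**What to change.** Change the hospitalization bullet in section 12.1:

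1. Label the existing analysis as time to first HF hospitalization and time to first cardiovascular hospitalization. In any set that includes patients who die, report cumulative incidence with death as a competing event in place of 1 minus Kaplan-Meier. The two agree where nobody dies. Kaplan-Meier stays for all-cause mortality.
2. Add total HF and total cardiovascular hospitalizations, patient-years from implant, and events per patient-year. Give the overall rate a 95% confidence interval that allows for within-patient clustering, for example a robust Poisson interval.
3. Show the counts by section 3.2 group descriptively, with a footnote that groups are assigned from later pacing. For the BiV Group the qualifying months are 10-12, so at a constant event rate 9/12 = 75% of counted events precede them.

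As a clarification, state whether the HF 30-day rate runs from implant or from an HF discharge.

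This needs no new data and only standard software. The cost is one or two extra descriptive tables, with by-group counts that cannot be read as effects of pacing.

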1.0 SYNOPSIS

Title:	MultiPoint™ Pacing (MPP) Post Market Study
Acronym:	MPP PMS
Purpose:	The purpose of this post market study is to characterize real-world use of MPP technology in patients indicated for a cardiac resynchronization therapy (CRT) device.
Objectives:	
The primary objective of this post market study is to understand the use of the MPP technology in real-world clinical practice. The study should provide an understanding of the impact of MPP technology on:
 
 • Overall CRT response rate measured by Clinical Composite Score (CCS). (A responder is defined as improved or unchanged from baseline and non-responder is defined as worsened from baseline.) • Quality of Life (QOL), left ventricular ejection fraction (LVEF, if available) and left ventricular end systolic volume (LVESV, if available) • Programming timing and workflow • Rates of heart failure (HF) hospitalization events, cardiovascular hospitalizations, and HF 30-day hospitalization rates • Costs associated with HF-related health care utilizations • All-cause mortality
Design:	
This is a prospective, multicenter, non-randomized registry/observational study. The study will enroll up to 2,000 patients with successful SJM CRT MP device implant from up to 140 centers undergoing CRT implantation. Any patient who received a market approved SJM Quadra Allure MP, Quadra Assura MP, or newer SJM CRT MP device is eligible for enrollment in the study. MPP programming guidance will be specified in the protocol. Patients will be followed for 12 months after implant. Data will be collected at Baseline (within 30 days prior to implant), Post-Implant (within 30 days following successful CRT device implant), 3, 6, 12 months and during any unscheduled follow-up visit.
 
[REDACTED]

Devices used:	Market-approved SJM Quadra Allure MP, Quadra Assura MP device, or newer SJM CRT MP device and market-approved SJM Quadripolar LV lead
Study Population	All subjects who meet inclusion criteria, do not meet exclusion criteria, sign an IRB/EC approved informed consent, complete a Baseline visit prior to device implant and have an attempted implant of the SJM Quadra Allure MP, Quadra Assura MP, or newer SJM CRT MP device will be considered

[figure not shown]
Clinical Investigational Plan

	enrolled in the study.

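### The HF 30-day hospitalization rate has no clock start, risk set or index rule, and its summary by section 3.2 group depends on later pacing, so it cannot be read as the impact of MPP

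*Combined protocol and SAP*

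**What the plan says.** Section 3.3 lists among the outcomes on which the study should show the impact of MPP: "Rates of HF hospitalization events, cardiovascular hospitalizations, and HF 30-day hospitalization rates". The synopsis carries the same item: "Rates of heart failure (HF) hospitalization events, cardiovascular hospitalizations, and HF 30-day hospitalization rates". Section 12.1 gives the method. Two of the three rates have a horizon: "Rates of heart failure (HF) hospitalization events at 12 months, cardiovascular hospitalizations at 12 months". The third has none: "HF 30-day hospitalization rates will be summarized using Kaplan-Meier method". Section 5.2 defines an HF event, including an HF hospitalization of at least 24 hours, but gives no 30-day rule.

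Section 12.1 also says that the objectives are summarized "by the groups defined in section 3.2". Section 3.2 defines those groups as follows:
- MPP Group: "MPP ON within 1 month post implant and then continuously programmed ON until 12 months".
- BiV Group: "MPP OFF at the 12-month study visit and for at least three continuous months prior to 12-month assessment".
- Treatment Strategy (BiV/MPP) Group: MPP on at the 12-month visit and for the three months before it, which the plan glosses as "BiV ON at some point in months 1-9 and MPP ON for months 10-12".
- Other Pacing Group: everyone else, categorized retrospectively.

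Section 5.5 leaves BiV and MPP programming to the physician at every visit.

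**The concern.** There are two gaps, and the second matters more.

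First, the endpoint is named but not defined. It could be an HF hospitalization in the 30 days after implant, or an HF readmission in the 30 days after an HF discharge. These have different clocks, denominators and typical sizes. Two analysts following section 12.1 could report different quantities under one label.

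Second, the stated grouping uses information from after the 30-day window. A 30-day event can happen early in the year, while membership of the BiV and BiV/MPP groups is settled by pacing in months 10-12. An HF admission is a natural occasion for reprogramming, so the outcome can help to determine the group it is counted in. A reader who takes group differences as the impact of MPP, as section 3.3 invites, could be misled in either direction.

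**Working it through.** The plan states no 30-day rate and the sample-size section is redacted, so there is no figure of its own to reproduce. All rates below are assumptions. Only N = 2,000 (section 3.2.1, the maximum) comes from the plan.

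**1. How far apart are the readings?** Assume a 12-month HF hospitalization risk r of 10% to 20% at constant hazard, and a 30-day readmission risk q of 10% to 25%.

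- Reading A, 30 days from implant with all implanted patients at risk: h = -ln(1 - r)/365 and risk = 1 - exp(-30h). For r = 10% the risk is 0.86%, about 17 patients. For r = 20% it is 1.82%, about 36 patients.
- Reading B, readmission within 30 days of a first HF discharge: index patients = 2,000 × r = 200 to 400, and the risk is q = 10% to 25%.
- Reading C, a 30-day readmission by month 12 over all implanted patients: r × q, from 0.10 × 0.10 = 1.0% to 0.20 × 0.25 = 5.0%.
- Ratio B/A: lowest 10%/1.82% = 5.5, highest 25%/0.86% = 29. Ratio B/C = 1/r = 5 to 10.

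**2. Is Kaplan-Meier itself the fault?** Take reading B with the clock at discharge, first readmission as the event, and 30-day death d of 1% to 10% as a competing event. With a = -ln(1 - q) and b = -ln(1 - d), cumulative incidence = a/(a + b) × [1 - (1 - q)(1 - d)].
- q = 10%, d = 1%: 9.95% against a Kaplan-Meier value of 10%, a gap of 0.05 points.
- q = 25%, d = 10%: 23.79% against 25%, a gap of 1.2 points.

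So Kaplan-Meier from discharge is serviceable. What is missing is the definition.

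**3. Grouping on the implant clock.** The window closes at day 30. The months that define the BiV and BiV/MPP groups begin after month 9, about eight months later. In the MPP Group, if MPP goes on at day 0, 7, 15 or 30, the share of the window before MPP is 0%, 7/30 = 23%, 15/30 = 50% or 100%. A patient on MPP in month 1 but off for months 10-12 meets the BiV definition.

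**4. Grouping on the discharge clock.** Consider patients discharged on BiV early in the year, with a true readmission risk q that pacing does not alter. Let s1 be the probability of a later lasting switch to MPP after a readmission, and s0 the probability without one. Among those who end in BiV/MPP, the observed risk is q·s1/[q·s1 + (1 - q)·s0]. Among those who end in BiV it is q(1 - s1)/[q(1 - s1) + (1 - q)(1 - s0)]. Both equal q only if s1 = s0. If readmission makes a switch more likely (s1 > s0), BiV/MPP looks worse and BiV better with no effect of pacing. Events that prompt turning MPP off work the other way. The plan gives no switching rates, so the size is unknown.

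**5. Requiring survival to 12 months.** The BiV and BiV/MPP definitions need a status at the 12-month visit. A simulation with no treatment effect (baseline 12-month death 8%, baseline readmission 20%, gamma frailty) compared all patients with 12-month survivors. At frailty CV 0.5, reading A moved from 1.31% to 1.30% and reading B from 23.2% to 23.1%. At CV 1.0 the moves were 1.30% to 1.20% and 30.6% to 29.8%. Under these inputs this effect is small.

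**6. Precision of reading B.** Exact 95% intervals at 20% observed: 4/20 gives 5.7% to 43.7%, 20/100 gives 12.7% to 29.2%, and 40/200 gives 14.7% to 26.2%.

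**The case against.** The strongest reply is that this is one of three rates in one bullet of a descriptive registry. No hypothesis is tested on it, a Kaplan-Meier estimate from HF discharge to first readmission is a standard quantity, and the fold differences come entirely from assumed rates. All of that stands. It limits the weight of the point, but supplies neither the missing definition nor a grouping fixed before the event.

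It is also fair that grouping by later pacing affects every by-group summary in section 12.1. The problem is still acute here, because a 30-day window can close months before the group is settled.

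Several stronger conclusions are tempting and are not supported:
- That the figure is uninterpretable on any reading. An overall risk from implant is readable, a first-readmission curve from discharge is valid, and reading C is also possible.
- That Kaplan-Meier can never count a readmission. This holds only for a first-admission curve started at implant, which section 12.1 does not specify for this item.
- That most patients lack their group's exposure in the first 30 days. The plan gives no switch-on dates, section 5.4.4 allows the post-implant visit on the day of implant, and BiV Group patients who never use MPP have their named exposure throughout.
- That a group difference cannot be due to MPP. The supportable statement is that the by-group figure cannot separate an MPP effect from the way the groups are formed.
- That an early discharge on BiV filed under BiV/MPP is mislabelled. That group is a treatment strategy that includes a BiV period. The difficulty is that the event may have caused the move into it and out of BiV.

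**Conclusion.** The point holds in two parts. The endpoint has no stated origin, risk set, index rule or handling of death, and plausible readings differ about 5- to 29-fold (implant against discharge) under the assumed rates. Those ratios are illustrative. More important, the plan's own rule of summarizing by section 3.2 group assigns a 30-day event according to later pacing, which the event may have prompted. That follows from sections 3.2, 5.5 and 12.1 without any assumed rate, although the size and direction of the distortion cannot be derived from the documents. The by-group figure therefore cannot serve as the impact of MPP named in section 3.3. This should be corrected before analysis. It makes one descriptive objective ambiguous and its group comparison misleading, but does not threaten an error rate.

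**What to change.** In section 12.1, section 3.3 and the synopsis, the sponsor should first confirm which quantity is meant.

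**If readmission:** the index is an HF hospitalization of at least 24 hours (section 5.2) with live discharge, the clock starts at discharge, and the event is a further HF hospitalization within 30 days. Report it overall and by pacing mode (MPP on or off) at the last interrogation before discharge, in place of the section 3.2 groups. Use either Kaplan-Meier from each patient's first index discharge, or events over all index discharges with a 95% confidence interval clustered by patient. Show death within 30 days separately.

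**If 30 days from implant:** report it overall. Any split should be by pacing mode when the clock starts.

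**Cost:** the change is mainly wording. Section 6.0 has a Health Care Utilization/Hospitalization CRF completed for each event, and sections 5.4.4 to 5.6 have device session records sent from scheduled visits and from unscheduled reprogramming visits. Two things need confirming: that discharge date and live-discharge status are captured, since the CRFs are held separately (Appendix F), and that discharge summaries are obtained, since section 6.0 lists them only as documents that may be sent. Index discharges will be few and intervals wide, and the grouping will differ from that of the other objectives. Pacing mode at discharge is still not randomized, so the comparison remains descriptive.
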